#### (h) Probable duration of study : one year

(i) Parameter/Variables to be measured: Age, sex, race, occupation, number of

warts, site of warts, response rate,

DLQI

- (j) Outcome measures : Response rate of warts to IL MMR and IL Vitamin D3
- (k) Statistical methods to be employed :
- a. **Data handling:** Data were entered in Microsoft Excel 2010 (Microsoft Corporation, Redmond, Washington, USA) and statistical analysis was done using Statistical Package for the Social Sciences 10.5 version (Chicago, Inc)
- b. Coding: Alpha numerical code was used
- c. **Monitoring:** Data was entered after every day of work and supervised by guide.
- d. Statistical analysis: will be conducted as per both per-protocol and intentionto treat population (defined as all enrolled patients to whom study drug will be given; with the last observation carried forward) basis using two sided tests.
  For *descriptive statistics*, percentage, mean, S.D., median, and minimum, maximum will be calculated along with graphical and tabular presentation.
  For *inferential statistics*, statistical methods that will be used are as follow
- Chi square test and Fisher's exact test to compare the categorical data between the groups.
- Paired t test for comparing normally distributed continuous variables (pretreatment and post treatment DLQI) at different time point within the groups.
- 3. Mann- Whitney U test to compare the not normally distributed variables (age,

duration of illness, size, number)

4. Kaplan–Meier curves to compare the response rate (complete, excellent, good or poor response) on each follow up visit (week 3, 6, 9, 12) between the groups.

Test of significance will be considered when value of  $p \le 0.05$ .

- (I) Ethical clearance : Will be obtained from the Institutional Review
   Committee (IRC), BPKIHS and Nepal Health
   Research Council (NHRC)
- (m) Permission to use copyright questionnaire/Proforma : N/A
- **11. For Intervention trial**
- a. Permission from Drug Controller of Nepal: not required
- b. Safety measure :will be applied
- c. Plan to withdraw : As per the decision of treating physician
- 12. Maintain the confidentiality of subject : Yes
- 13. References : attached
- 14. Whether available resources are adequate: adequate
- **15. Other resources needed** : not needed
- 16. Cost involved (Approx in NRS)
- a. Investigations :60,000 (approximate)
- b. Surgery :NA
- c. Drugs :64,500 (approximate)

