### Intralesional MMR vaccine

The mechanism of action of intralesional MMR immunotherapy is still an enigma. Some authors hypothesize that it acts through the induction of a strong nonspecific inflammatory response against the HPV-infected cells. It has also been suggested that the trauma itself may cause wart clearance in previously sensitized individuals. The cytokines produced by immune system such as interleukin (IL)-2, IL-4, IL-5, IL-8, interferon (IFN)- $\gamma$  and tumor necrosis factor (TNF)- $\alpha$  stimulate a strong immune response against HPV may be another possible mechanism of action. Another author reports that the response to antigen injection was associated with the proliferation of peripheral blood mononuclear cells that promotes Th1 cytokines including IFN- $\gamma$  and IL 2, which further activate cytotoxic T cells and natural killer (NK) cells that eradicate HPV-infected cells.

Subjects can be tested for existing immunity by intrademal injection of 0.1 mL of MMR vaccine into the skin of the forearm. Determination of a positive reaction requires erythema and induration of at least 5 mm in diameter within 48–72 hours. Patients reactive to the skin test are labelled responders and IL MMR is more effective in them.

**Nofal A et al** conducted a randomized controlled trial (RCT) with 135 patients of which 85 patients received the MMR vaccine and 50 received Normal saline as control. Both treatment groups were injected in single largest wart at 2 weekly intervals until complete clearance for a maximum of 5 treatment and were followed up bimonthly for 6 months. In the MMR group, complete response was achieved in 80% and 84.6% of patients presenting with recalcitrant and multiple warts respectively. No recurrence was observed in the MMR group and side effects included pain during injection and flu-like symptoms.

Author	Setting	Type of	Sample	Type of	Percentage of
		Study	size	wart	complete clearance
Nofal A and	Zagazig University,	Randomize	135	Common	Recalcitrant wart-
Nofal E,	Egypt	d controlled		warts	80%
2010 		trial			Multiple Wart-84.6%
Nofal A et al.	Zagazig University,	Prospective	65	recalcitran	63%
2015 	Egypt			t wart	
Naseem R	Federal	Prospective	170	Common	81.3%
and Aamir S,	postgraduate			warts	
2013 	medical Institute &				
	Sheikh Zayed				
	Hospital, Lahore,				
	Pakistan				

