In a case report done by **Jakhar, Kaur, and Misri** in 2018, the injection was given at a dose of 0.1 mL/cm2 just beneath the wart. A maximum of 0.4 mL was used in a single session in cases of multiple warts. The session was repeated at 2-week intervals for a maximum of 4 sessions or complete resolution of warts, whichever is earlier. The resolution of warts typically started in 7 to 10 days, and warts are shed spontaneously within 4 to 6 weeks. The only side effect was pain during injection, which was minimized with a dose of lidocaine before injection with vitamin D3. Two to 4 sessions are usually required on average for complete cure.

**Raghukumar et al.** conducted a study in 2017 in 64 patients with recalcitrant warts. Complete response with IL vitamin D was seen in 54 of 60 (90%), partial response in 4 of 60 (6.66%), and no response in 2 of 60 (3.33%). The average number of injections required to achieve a complete resolution was 3.66. Complete resolution of distant warts was noticed in all patients.

**Kareem et al.** conducted RCT in 50 patients who were divided into two groups: thirty patients as cases group who received an intralesional injection of 0.2 ml of vitamin D3 (300.000 IU) and another twenty patients as a control group who were injected with normal saline solution. Standardized photographs were taken before, one month and three months after the procedure. The degree of the response was classified into complete, partial and no response. Complete clearance of the target injected warts was seen in 40% of patients in the cases group and 5% of patients in the control group (P≤0.001) that was statistically significant.

Similarly, in a study conducted by **EI-Taweel et al.** 20 patients with verruca vulgaris and deep palmoplantar warts were included. Forty percent of the lesions treated with IL vitamin D3 showed complete clearance and the rate of distant wart response was 17.65%. Among different demographic and clinical variables in the studied patients, smoking and older age seemed to decrease the therapeutic response 

In a prospective study conducted by **Shilpa et al** on 2019, 33 of 42 patients (78.57%) showed a complete response, 6 patients (14.28%) showed moderate response and three patients (7.14%) showed mild response with IL vitamin D3. Recurrence was observed in one patient with the palmoplantar wart. No serious adverse effects were reported.

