### Sample size

The study considers a 95% confidence interval, 80% power to estimate sample size. According to the literature review, it was found that 84.6% and 40% improvement were seen with IL MMR and IL Vitamin D respectively.

Now using the sample size estimation formula for 2 proportion

```
Now using the sample size estimation formula for 2 proportion

n = 2p(1-p) (Z\beta + Z\alpha/2)^2
```

n= sample size for each group

 $p_1 = 0.846$ 

 $p_{2} = 0.40$   $p = (p_{1} + p_{2})/2$   $Z_{\alpha/2} = 1.96 \text{ at } 95\% \text{ CI}$   $Z_{\beta} = 0.842 \text{ at } 80\% \text{ power}$ Using above formula, n= 18.54 Considering loss of follow up, sample size in each group= 30 Total sample size= **60** 

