#### Statistical analysis

- Data handling: Data will be entered in Microsoft Excel 2010 (Microsoft Corporation, Redmond, Washington, USA) and statistical analysis will be done using Statistical Package for the Social Sciences 10.5 version (Chicago, Inc)
- 2. Coding: Alpha numerical code will be used
- Monitoring: Data will be entered after every day of work and supervised by guide.
- 4. Statistical analysis will be conducted as per both per-protocol and intention-to treat population (defined as all enrolled patients to whom study drug will be given; with the last observation carried forward) basis using two sided tests.

For *descriptive statistics*, percentage, mean, S.D., median, and minimum, maximum will be calculated along with graphical and tabular presentation.

For inferential statistics, statistical methods that will be used are as follow

- a. Chi square test and Fisher's exact test to compare the categorical data between the groups.
- b. Paired t test for comparing normally distributed continuous variables (pretreatment and post treatment DLQI) at different time point within the groups.
- c. Mann- Whitney U test to compare the not normally distributed variables (age, duration of illness, size, number)
- d. Kaplan–Meier curves to compare the response rate (complete, excellent, good or poor response) on each follow up visit (week 3, 6, 9, 12) between the groups.

Test of significance will be considered when value of  $p \le 0.05$ .

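### The only analysis that names response applies Kaplan–Meier to four ordered grades with no event, censoring rule or test, and does not match the two-proportion sample size

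*Combined protocol and SAP*

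**What the plan says.** - **Outcome.** Item 10(j) of the summary gives the outcome measure as "Response rate of warts to IL MMR and IL Vitamin D3". No grade, visit or rater is attached. The third primary objective is to compare the efficacy of the two treatments.
- **Method that names response.** To set the two arms against each other, item d of Statistical analysis, repeated in item 10(k) of the summary, plans "Kaplan–Meier curves to compare the response rate (complete, excellent, good or poor response) on each follow up visit (week 3, 6, 9, 12".
- **General categorical method.** Item a plans "Chi square test and Fisher's exact test to compare the categorical data between the groups", without saying which variables it covers.
- **Populations.** The analysis is to be "conducted as per both per-protocol and intention-to treat population". Neither population is called primary. The missing-data rule is last observation carried forward, and tests are two-sided.
- **Sample size.** It rests on the statement that "84.6% and 40% improvement were seen with IL MMR and IL Vitamin D respectively", followed by "Now using the sample size estimation formula for 2 proportion".
- **Grades and raters.** Table 3 under Operational definition sets four grades from complete (100%) to poor or none (0–49%), scored by patient and physician. Complete response there includes distant warts.
- **Visits.** There are up to five sessions three weeks apart, then monthly follow-up for three months to detect recurrence. The proforma's follow-up table (visits 6 to 8) has a field for percentage decrease from baseline.

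**The concern.** Item d is the only place where the outcome meets an inferential method, and the two do not fit. A Kaplan–Meier curve estimates the time to one defined event. Four ordered grades recorded at each visit are not an event, and poor or no response cannot be an event alongside complete response. The item has no censoring rule. Carrying the last observation forward is not one: it treats a dropout as still observed, whereas censoring removes that patient from the risk set. A pair of curves is also only a description until a test or an effect estimate is attached.

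The sample size assumes a different analysis, a comparison of two proportions. An analyst who sets item d aside and turns to item a must still choose the cut-off, the visit, whose rating counts and which population leads. Two analysts could follow the text faithfully and report different primary results from the same data, and a reader could not tell whether the choice came before or after the data were seen.

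**Working it through.** **1. What the sample size assumes.** Inputs from Sample size: p1 = 0.846, p2 = 0.40, Z = 1.96 and 0.842. The denominator is missing from the formula as extracted, but (p1 − p2)² is needed to reach the stated figure.

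- Mean proportion: (0.846 + 0.40)/2 = 0.623
- n = 2 × 0.623 × 0.377 × (1.96 + 0.842)² / (0.846 − 0.40)²
- n = 0.4697 × 7.851 / 0.1989 = 18.54 per group

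This reproduces the plan's 18.54, which it raises to 30 for loss to follow-up. The arithmetic is sound. What matters is that it sizes a binary comparison.

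**2. Which binary endpoint the rates describe.** Sample size calls both rates improvement. The plan's own literature review is more specific:

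- MMR: "complete response was achieved in 80% and 84.6% of patients presenting with recalcitrant and multiple warts respectively"
- Vitamin D: "Complete clearance of the target injected warts was seen in 40% of patients in the cases group"

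Both are complete-response or clearance rates, so the sizing points to complete response. It does not settle the endpoint, because the 40% concerns injected target warts while complete response in Table 3 includes distant ones.

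**3. What item d supplies against what it needs.**

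| Needed | In item d |
|---|---|
| One event | No: four grades, including poor |
| Time to event | Visit weeks only; no origin or event time |
| Censoring rule | None |
| Test or effect estimate | None |

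**4. What item a leaves open.** The grades are categorical, so chi-square or Fisher can be applied to them. Nothing fixes the cut-off, the visit, the rater or the leading population.

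**5. Timing.** If the first session is at week 0 (implied by the schedule, not stated), five sessions fall at weeks 0, 3, 6, 9 and 12. Week 12 is then the fifth-session visit, and a rating made before that injection reflects at most four sessions. Item d has no assessment after a fifth session. Assuming a constant chance of clearance per session, the rate after four sessions is 1 − (1 − F)^(4/5):

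- MMR: 0.846 becomes 0.776
- Vitamin D: 0.40 becomes 0.335
- Difference: 44.6 points becomes 44.1; Fisher power with 30 per arm goes from 93.5% to 91.3%

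Under that assumption the effect is small.

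**6. Does one binary comparison fit the planned size?** Power at 0.846 against 0.40, two-sided 0.05:

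| Per arm | Chi-square | Fisher (exact enumeration) |
|---|---|---|
| 30 | about 96% | 93.5% |
| 19 | 83.8% (normal approximation) | 77.3% |

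At the plan's own rates, a single complete-response comparison needs no change in the number of patients.

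**The case against.** The strongest reply is that the comparison can be inferred. Table 3 defines categorical grades, item a compares categorical data between groups, and the trial is sized on complete-response proportions. Chi-square or Fisher on complete response is then the natural reading, with item d as a descriptive addition. Much of this stands. A reader might infer that the plan contains no usable test for response; the documents do not support that, because item a can serve. What the reply does not supply is a visit, cut-off, rater or primary population, and it does not make item d workable.

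Other strong readings also fail:

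- **That naming both chi-square and Fisher leaves the result open.** By the usual convention Fisher is used only when an expected count is below 5. At 30 per arm, tables on which the two tests disagree practically never have such a count, so the convention settles the choice. The plan should still state it.
- **That the choice of rater changes the result by a known amount.** The documents give no rate of disagreement between patient and physician. The single unlabelled percentage field on the proforma could hold a joint score, and that table was poorly extracted.
- **That testing at four visits inflates false positives.** This would need a rule of claiming success at any visit, and the plan states none.
- **That the three-month follow-up visit must be primary.** Follow-up is there to detect recurrence. Counting recurrence as failure would depart from the clearance rates used for sizing, and carrying forward the grade of a cleared patient who drops out would hide a relapse.

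**Conclusion.** The concern holds, and it should be fixed before any outcome data are examined. Item d is not merely short of detail: the stated method cannot make the comparison in the third primary objective, and it does not match the analysis for which the trial was sized. Item a offers a suitable family of tests but leaves cut-off, visit, rater and primary population open.

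The effect on the result cannot be quantified from the documents, and the conclusion does not depend on a figure. The power of about 96% or 93.5% rests on the plan's rates and on 30 analysed per arm. It shows that a well-defined comparison is feasible, not that those rates will be seen. The timing point is minor and assumes a first session at week 0. The sample-size arithmetic is not at fault.

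**What to change.** In Statistical analysis and in item 10(k) of the summary, name one primary comparison:

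- **Endpoint:** proportion with complete response (100%, Table 3), by physician assessment against the baseline photograph.
- **Visit:** one fixed visit after the last session. The first monthly follow-up visit (visit 6) suits this, since the proforma already records percentage decrease there. No photograph is scheduled at that visit, so the physician would compare the patient directly with the baseline image.
- **Population:** intention-to-treat as the plan defines it, with its existing missing-data rule.
- **Test:** chi-square, or Fisher's exact if any expected count is below 5, with a risk difference and 95% confidence interval.

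Keep Kaplan–Meier only for time from first session to first complete response, with a log-rank test and censoring at the last visit attended. Report the four grades by visit descriptively. Make these secondary or sensitivity analyses: the patient's rating, the per-protocol population, missing counted as non-response, and sustained response or recurrence at visit 8.

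**Cost.** Wording in two places and a rater label on the proforma; no new visit, photograph or patient. Visit 6 fits the one-year study: 26 weeks of enrolment + 12 weeks to the fifth session + about 4 weeks = 42 weeks. One limitation should be stated: patients who clear early stop treatment early and reach their first follow-up visit sooner, so the visit is fixed relative to the last session and not to the start of treatment.

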In a prospective study conducted in the Dermatology outpatient department of V.S Hospital, Ahmedabad by **Shah A et al** over a period of one year patients received

intralesional MMR vaccine 0.5ml into a single wart or the largest wart in case of multiple lesions at an interval of two weeks for three treatments. The response was evaluated as 0-49% as no response, 50-99% as partial response and 100% as complete response. Follow up was made every 02 weeks for 06 weeks and then monthly for 06 months to detect any recurrence. They found complete response was seen in 36 (72%), partial response in 08 (16%) and no response in 06 (12%) patients. No recurrence was observed. Pain at the site of injection in 18 (36%) and the flu like symptoms in 02 (04%) patients were observed. 

In 2016 **J Raju et al** injected MMR vaccine into the largest single wart intralesionally and gave subsequent injections every 2 weeks apart for about 3 to 5 times and obtained complete remission of warts in 70.4% of patients, partial remission in 22.2% and no response in 7.4% of patients. 

**Vontela R et al** observed complete clearance in 72% patients and partial clearance in 16% of patients receiving the MMR vaccine. No response is seen in 12% of patients. The recurrence rate during the 6 months follow up period is 12%. Pain during injection was noted in 60% of patients without any other adverse effects in the treated patients. The mean duration taken to show the complete clearance of the lesions is 9 weeks

In 2017 **Chauhan et al** injected 0.25 mL MMR vaccine intralesionally in the largest wart and repeated at 2-week interval until complete clearance or a maximum of five doses. They evaluated outcome as complete clearance, excellent, good, or unsatisfactory response on a visual analog scale at every visit

and at 4 and 8 weeks, thereafter by comparing baseline clinical photographs. They used a Likert scale for patient satisfaction level assessment similarly. Out of 51 patients who completed the study 42 (82.4%) of them showed complete clearance of warts and 9 (17.6%) patients showed good or unsatisfactory response. In 4 (7.8%) patients, warts subsided completely after one dose itself. The four patients showing an excellent response after five doses initially also continued to improve during a follow-up period of 8 weeks. Except for injection site pain, no adverse effects were noted. There was no recurrence of warts among them.

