### Group A

Freeze-dried MMR vaccine single-use vials stored at 2°C–8°C will be reconstituted with 0.5 mL of provided diluent (distilled water) as per manufacturer's instruction immediately before intralesional use. If reconstituted vaccine is not used within 8 hours it must be discarded. All Group A patients will

receive intralesional injection of upto 0.5 mL of reconstituted MMR vaccine into a single or a maximum of 5 warts at a time in case of multiple warts with 31 G insulin syringe with beveled edge facing upward. Amount of injection on each wart will depend on the size of each wart. The intralesional injection will be given every three weeks for a maximum of 5 doses or until complete resolution, whichever is earlier.

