#### **Group B**

All Group B patients will receive a maximum of 0.5 mL Inj. Vitamin D3 (600,000 IU; 15mg/ml) in each session after injection of IL lignocaine with 31 G insulin syringe. In cases of multiple warts, a maximum of 5 warts will be injected at a time. Amount of injection on each wart will depend on the size of each wart. The session will be done at 3 weekly intervals for a maximum of 5 sessions or until complete resolution of warts, whichever is earlier. 

Patient and physician global assessment using 'Visual Analog Scale score' and photographic comparison will be used to assess decrease in size and number of warts and thus the response to treatment. The clinical improvement will rated as complete response, excellent response, good response, poor or no response by the patient and physician global assessment using visual analog scale score at each visit taking baseline clinical photograph as controls. Immediate and late adverse effects of MMR vaccine and Vitamin D will be evaluated after each treatment session. Necessary investigations and intervention will be done if needed. Follow up will be made monthly for three months to detect any recurrence.

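### The only analysis that names response visits ends at week 12, the fifth-dose visit, and no response reading after the full course is specified

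*Combined protocol and SAP*

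**What the plan says.** **Treatment schedule.** In Group A the injection is "given every three weeks for a maximum of 5 doses or until complete resolution, whichever is earlier". Group B follows the same pattern: "The session will be done at 3 weekly intervals for a maximum of 5 sessions", again ending early if the warts resolve.

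**Response rating.** Methodology (text under Group B) has the patient and the physician grade response by "global assessment using visual analog scale score at each visit taking baseline clinical photograph as controls". The grades, from complete to poor or none, are in Table 3.

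**After treatment.** The same section says: "Follow up will be made monthly for three months to detect any recurrence". The proforma treats visits 1 to 5 as treatment visits and 6 to 8 as follow-up. It has a column for percentage reduction since baseline at visits 6 to 8 as well. A photograph is also planned three months after the last session (Methodology).

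**Analysis.** Item d of Statistical analysis, repeated in section 10(k) of the summary, uses Kaplan–Meier curves to compare response grades "on each follow up visit (week 3, 6, 9, 12) between the groups". Item a applies chi-square and Fisher tests to categorical data in general, without naming response or a visit. No primary time point is given anywhere.

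**The concern.** The primary objectives are the efficacy of each treatment and the comparison between them, and each treatment is a course of up to five sessions. If the last response reading is taken on the day of the fifth session, a patient who needs the whole course is judged before the course can have worked. That patient is graded below complete response in either arm, whatever happens next.

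Two things are at stake. The clearance rate reported for each regimen would be that of a course cut short for the slower responders. And because response is also recorded at visits 6 to 8 with no primary reading named, the headline comparison could be made at week 12 or at any of three later visits, with the choice open until the data have been seen.

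**Working it through.** **Inputs.** Three-week spacing and a maximum of five sessions (Group A, Group B); response visits at weeks 3, 6, 9 and 12 (item d); monthly follow-up for three months (text under Group B). Assumptions: the first session is week 0, and the monthly visits are counted from the last session in four-week months. The first fits the proforma, since four readings after baseline match visits 2 to 5.

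**Step 1: dose dates.** Dose k falls at week 3 × (k − 1). The first follow-up visit after a full course (visit 6) is at week 12 + 4 = 16; visits 7 and 8 are at weeks 20 and 24.

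| Dose | Given at week | Weeks observed at week 12 | Weeks observed at visit 6 (week 16) |
|---|---|---|---|
| 1 | 0 | 12 | 16 |
| 2 | 3 | 9 | 13 |
| 3 | 6 | 6 | 10 |
| 4 | 9 | 3 | 7 |
| 5 | 12 | 0 | 4 |

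**Step 2: what dose 5 can contribute by week 12.** Dose 5 is given only to a patient who has not completely resolved, so everyone who receives it is short of complete response at that visit. Its contribution to complete response in item d is therefore nil in both arms. This follows from the stopping rule alone and needs no assumption about how fast either agent works.

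**Step 3: when the plan's sources read response.** The MMR study that supplies the grading scale in Table 3 also rated patients 4 and 8 weeks after treatment, and four with an excellent response after five doses "continued to improve during a follow-up period of 8 weeks". The vitamin D trial behind the 40% planning rate took photographs one and three months after the procedure.

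**Step 4: what an early reading could cost.** The plan's sample size reproduces, using its formula with the squared difference in rates as denominator. With p = (0.846 + 0.40)/2 = 0.623:

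n = 2 × 0.623 × 0.377 × (1.96 + 0.842)² / (0.846 − 0.40)² = 3.688 / 0.1989 = 18.54 per group, raised to 30.

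This figure does not depend on the present point. For illustration only, suppose week 12 shows a fraction f of final clearance, the same in both arms, with all 30 per arm evaluable. Then, with d = f × (0.846 − 0.40), p₁ and p₂ the reduced rates and p their mean,

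power = Φ{[d√30 − 1.96√(2p(1 − p))] / √[p₁(1 − p₁) + p₂(1 − p₂)]}.

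| f | MMR | Vitamin D | Difference | Power |
|---|---|---|---|---|
| 1.0 | 84.6% | 40.0% | 44.6 points | 0.965 |
| 0.9 | 76.1% | 36.0% | 40.1 points | 0.90 |
| 0.8 | 67.7% | 32.0% | 35.7 points | 0.805 |
| 0.7 | 59.2% | 28.0% | 31.2 points | 0.69 |

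The documents give no value for f.

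**The case against.** The strongest reply is that nothing is actually excluded. Item a covers categorical data with no limit on visits, the response grade is categorical, and the follow-up visits record percentage reduction. An end-of-follow-up comparison is therefore allowed. This stands: a reader might infer that later response is shut out of the efficacy answer, but the text supports only that no analysis specifies it.

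Second, five sessions is a maximum. One cited vitamin D study needed 3.66 injections on average, and one cited MMR series reports a mean of 9 weeks to clearance. Many patients may be clear before week 12, and for them the reading is adequate unless they recur. This limits how many patients are affected, but does not help those who need the whole course.

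Three further inferences are tempting and should not be drawn:

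- **That most of the effect of dose 4 is missed, or that only three of the five doses have had time to act.** This rests on the statement "warts are shed spontaneously within 4 to 6 weeks". It comes from a single vitamin D case report with two-week intervals, which also puts the start of resolution at 7 to 10 days. The protocol does not say whether the 4 to 6 weeks run from each injection, and nothing extends them to MMR.
- **That 2 to 3 of 30 patients per arm would be under-graded.** This takes the four late improvers among 51 MMR patients (4/51 = 7.8%; 0.078 × 30 = 2.4). They are reported as improving, not as cleared, and after a two-weekly course. The rate cannot be carried over to vitamin D. The 7.8% printed in the protocol describes a different group, those cleared after one dose.
- **That week 12 favours the faster agent.** It would if the arms differed in speed, but the documents do not show that they do.

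**Conclusion.** The concern holds in a limited form. The only analysis with named response visits ends on the fifth-dose day. Dose 5 cannot contribute a complete response to it, dose 4 has three weeks of observation, and no reading after the full course is specified although the data will be collected. This is more than a missing detail, because the visit list as written gives a truncated answer to the primary question.

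The size is known only in terms of the schedule: zero weeks of observation for dose 5 and three for dose 4. The number of late responders and any difference between arms are not in the documents, so bias in the comparison is possible but not shown. The power table in the working depends on an assumed fraction and shows sensitivity, not an expected loss. The dates rest on taking the first session as week 0; the point about dose 5 also takes week 12 as its injection day, but does not depend on whether rating precedes or follows the injection that day.

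**What to change.** In Statistical analysis and in section 10(k) of the summary:

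1. Name one primary response reading: complete response at visit 6, defined as one month after the last session, compared between arms by chi-square or Fisher's exact test.
2. Grade each patient on status at that visit, so that a patient who cleared but has recurred by then does not count as a complete response.
3. Report the 3-month visit, with its planned photograph, as a secondary reading of sustained response.
4. Keep weeks 3, 6, 9 and 12 as secondary readings of speed of response.

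The cost is wording only. The visits, the percentage field and the photograph are already planned. There are two small downsides. Dropout before visit 6 may be somewhat higher than at week 12; under the plan's last-observation rule those patients would keep an earlier grade, so their number should be reported by arm. Visit 6 will also fall at different calendar weeks for patients who stop early, which should be stated when the results are presented.
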